9.2. Risks and side effects

As the project is mainly observational and contains no interventions the overall risk for the subject is extremely limited. No changes/adjustments in medication will be made and there will be no risk for hypo/hyperglycemia. The main issue for the participants is the fact that some time is needed for the conduction of the examinations. Furthermore, a small amount of transient pain might be felt during some of the examinations; however, no lasting side effects are reported regarding any of the examinations. To minimize the risk of side effects the examinations will be conducted by trained personnel, and all equipment will be solely tested before usage on participants.

Different measurements may possibly reveal pathological conditions among subjects. The participants will be informed that the study might find additional medical conditions and they will be given the choice whether to be informed or not if this is the case. All findings, which are categorized "abnormal" or outside the normal range will be conferred with a medical doctor involved in the study, who will decide the plan and inform the subject of this. This might lead to further examinations, which will be offered to the subject. If the subject has declined the opportunity to receive any information, this will be respected.

Listed below are the potential risks and side effects of the different examinations included in the protocol:

- **Blood and urine samples:** Almost negligible risk of infection, small bleeding, or pain around syringe insertion. 88 ml blood will be taken from each participant including screening samples. If subjects consent for samples for the biobank for future research projects, additionally 24 ml of blood will be taken, bringing the total amount of blood taken to 112 ml. If any blood samples come back with elevated or potentially dangerous results, the staff will act accordingly and discuss these findings with a medical doctor. No side-effect regarding urine samples.
- **DXA and HR-pQCT:** The risks of adverse reactions from the DXA or the HR-pQCT scans are minimal due to the low dose of radiation applied through the test. In theory this will increase the life-time risk of cancer from approximately 25% to less than 25,00002 %. No children or pregnant women are included in the project. The DXA scan may show sign of osteoporosis, which is an asymptomatic condition, mostly diagnosed after a fracture have occurred. Thus, it will be an advantage for subjects to have this diagnose assessed prior to any fracture occurrence. If osteoporosis is diagnosed, they will be referred to their general practitioner for further assessment and treatment.
- **Microindentation:** Participants will experience slight discomfort from microindentation due to localized pain in relation to the insertion site and, rarely, hematoma. Complications such as hematoma from microindentation are rare. There is a small risk of infection and reaction to local anesthesia such as redness, itching and subcutaneous hematomas. **PTT:** Participants might feel a small amount of transient pain during the examination. No lasting pain will occur.

- **Skin biopsy:** Participants might feel a small amount of transient pain during and a small bleeding. No lasting pain will occur. There is a small risk of infection and reaction to local anesthesia such as redness, itching and subcutaneous hematomas.
- **OCT, Fundus Photography and visual examination:** It is a common procedure performed by trained personnel. Eyes will not be dripped.
- **Vital signs and body measurements, 12-lead ECG, skin AGE Reader, Vagus™, QST, NC-stat DPNCheck, force platform, gait function and muscle strength assessments:** No risks or side-effects.

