4.2. Study population

The study strives to include a total of 300 subjects with T2D divided into three well-defined groups:

- T2D F-/N-: Subjects with T2D and no previous history of any fractures or diabetic neuropathy ($n=160$)
- T2D F+: Subjects with T2D with a previous history of a fracture(s) (any fracture, major osteoporotic fracture (MOF) and peripheral) ($n=100$)
- T2D N+: Subjects with T2D matched by age and sex with severe peripheral (vibration perception threshold (VPT) > 50) or a history of autonomic neuropathy ($n=40$).

[figure not shown]

Figure 2: Study design

Inclusion criteria

1. Men and women with minimum 40 years of age.
2. Diagnosis of T2D. At least one of the following criteria must be met at diagnosis:
 - a. HbA1c ≥ 48 mmol/mol (6,5 %)
 - b. Plasma glucose $\geq 11,1$ mmol/l
 - c. Fasting plasma glucose $\geq 7,0$ mmol/l
3. Clinical effect of oral antidiabetic medication strengthens the diagnosis.
4. Diagnosis of diabetes at least one year prior to inclusion of the study.
5. A history of fracture(s) (confirmed by radiographs analyzed by radiologist) following the diabetes diagnosis (T2D F+ group)
6. Diagnosed with severe peripheral (VPT ≥ 50) or autonomic neuropathy defined by cardiac autonomic reflex tests or severe abnormalities in orthostatic blood pressure (T2D N+ group)
7. Signed the informed consent.
8. Not defined by the exclusion criteria.

Exclusion criteria

1. Severe decreased liver function (Alanin amino-transaminase (ALAT) >250 U/l, Gamma-Glutamyltransferase (GGT) >150 U/l).
2. Moderate to severe kidney dysfunction, estimated Glomerular Filtration Rate (eGFR) <15 mmol/L/1,73m².
3. Pregnancy or breast feeding.
4. Active malignancy or terminal ill.

5. Previous chemotherapy or immunomodulating treatment
6. Known severe vitamin deficiency
7. Current or previous alcohol- or drug abuse.
8. Not being able to understand Danish written and/or verbally.
9. Terms according to investigators judgement that makes subjects unsuitable to participate including lack of ability to understand and comply with instructions and/or reduced physical ability, limiting the ability to participate in the examinations.
10. Participating in other clinical studies utilizing experimental treatment or medication.
11. Subjects with pathologic fractures (defined as fractures due to local tumors, tumor-like lesions, or focal demineralization as visualized on radiographs).

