12. Primary hyperparathyroidism, Paget's disease and other metabolic bone diseases, uncontrolled thyrotoxicosis, celiac disease not controlled by diet, known hypogonadism, severe COPD, hypopituitarism, Cushing's disease.
13. Fracture < 6 month ago
14. Initiation of antiresorptive or bone anabolic drugs <12 months ago to ensure stable bone turnover markers.
15. History of fractures following the diagnosis of diabetes (T2D F-/N- and T2D N+ groups).
16. History of peripheral or autonomic neuropathy defined by cardiac autonomic reflex tests or severe abnormalities in orthostatic blood pressure (T2D F-/N- group).
17. Suspected peripheral or autonomic neuropathy of other causes than diabetes (e.g., concomitant central nervous system pathologies).
18. Known peripheral arterial disease (PAD) defined as toe pressure <40mmHg, no palpable foot pulses or clinical claudicatio intermittens.
19. Active diabetic foot ulcers at time of inclusion.
20. Previous or expected amputations in lower extremities, of any cause, during the study.
21. Known allergy to lidocaine.

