4.5. Study procedures

General health data from medical records and interview

To enable the best possible adjustment of confounding factors in later analysis, general health information for each subject will be assessed through medical records and interviews. These include assessment of weekly alcohol consumption, daily tobacco use, daily activity level (at work and at home), comorbidities, signs and symptoms of neuropathy, familiar disposition to osteoporosis, risk factors/comorbidities associated with osteoporosis in accordance with the National treatment guideline in Endocrinology (NBV), prior biochemistry, duration of diabetes, prior fractures (localization, high/and medication use (including hormone therapy such as oral contraceptives etc.) for at least one month prior to baseline measurements.

Laboratory assessments

Individual laboratory values will be compared to their relevant reference range (when existing) and flagged as being below or above the range. The blood samples will be taken and handled as usual by the Research bio. Med. Lab. technologists at Aalborg University Hospital.

If laboratory samples need to be re-done, due to missing results (e.g., hemolysis, sample leaked, inconclusive, lost in transit etc.), the subject should be called in for resampling. Final laboratory reports must be reviewed, dated, and signed by the investigator on the day of evaluation. It must be specified by the investigator whether out of range results are clinically significant. The subjects are allowed to receive or betray results (See informed consent form).

Biochemistry:

The following samples will be taken at the screening visit (total 4 ml):

- Creatinine, eGFR
- ALAT
- Gamma-Glutamyltransferase
- TSH
- 25-hydroxy D-vitamin
- Cobalamin

The following samples will be taken at the study day (total 84 ml including samples for the research biobank):

- HbA1c
- Fasting-C-peptide and fasting P-glucose (for HOMA2-%B and -IR)
- CRP
- Lipids (LDL, HDL, total cholesterol, triglycerides)
- PTH
- Calcium
- Phosphate
- Magnesium
- Carbamide
- Sodium
- Potassium
- Alkaline phosphatase
- Bilirubin
- Albumin
- M-component
-
- Hematology
 - Hemoglobin
 - Erythrocytes
 - Reticulocytes
 - Hematocrit
 - Middle Cell Volume
 - Middle Cell Hemoglobin Concentration
 - Leukocytes and diff. counting
 - Thrombocytes
 - Folate
 - Ferritin
 - Transferrin
- hsCRP*
- FGF23*
- Sclerostin*
- Osteoglycin*
- Osteocalcin*
- Undercarboxylated osteocalcin (ucOC)*
- Osteopontin*
- P1NP*

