- CTX*
- EsRAGE*
- GIPR*
- Testosterone/estradiol *

- FSH*
- LH*
- Adiponectin*
- Leptin*
- IGF-1*

*: The sample will be analyzed after study completion from blood stored in the research biobank (see section 7.2)

Estimated time: 10 min

24-hour urine collection:

- Creatinine
- Carbamide
- Sodium
- Potassium
- Volume
- Protein
- Albumine
- Ratios

Assessment of vital signs and body measurement

Cardiovascular parameters including heart rate, systolic and diastolic blood pressure. This will be assessed using an Electronic Blood Pressure Device (Omron M6 Comfort IT Intelligence) after 5 min of quiet sitting. Blood pressure will be measured three time and the mean value will be calculated of the last two measurements. If the subject is using antihypertensive medication to control blood pressure, then the medication should be taken as usual prior to assessing vital signs.

Height: (Without shoes) will be measured and rounded to the nearest half centimeter.

Body weight: Should be measured in kilograms (kg) without overcoat and shoes and wearing only light clothing. Body weight will be recorded to one decimal place.

BMI is calculated.

Estimated time: 10 min.

Orthostatic blood pressure

After the normal blood pressure procedure, the subjects will be asked to stand for three minutes and afterwards a new blood pressure will be measured.

Orthostatic hypotension is defined as a decrease in systolic blood pressure of 20 mmHg or a decrease in diastolic blood pressure of 10 mmHg within three minutes of quiet standing when compared with blood pressure from the sitting position.

Estimated time: 5 min.

12 lead-Electrocardiogram

An ECG-12 lead will be performed in a lying position and the subject will have bare chest. The ECG must be interpreted by the investigator and documented.

The evaluation must follow the categories:

- Normal
- Anormal
 - o Clinically significant? (Yes/no)

ECG findings will be summarized descriptively. If an ECG-12 lead has already been performed within three weeks before entering the trial and if the results are available, the procedure does not need to be repeated. However, if clinical warranted as judged by the investigator the ECG-12 lead should be repeated.

Estimated time: 10 min.

DXA scan

Will provide BMD at the hip and spine, TBS (trabecular bone score) and body composition measures (lean body mass, fat mass and distribution, muscle mass).

Overview

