9.1. Informed consent

Subjects interested in participating in the study will receive written information about the project ("Dine rettigheder som forsøgsperson i et sundhedsvidenskabelig forskningsprojekt" produced by *Den National Videnskabsetiske Komité (NVK)*) and a folder of the study ("deltagerinformation"). If the subject is interested in participating in the project after reading the written information, they will be asked permission to access medical records for screening in accordance with the Danish law. Medical records will be assessed for information on comorbidities and diabetes complications, relevant diagnostic imaging, medications, and previous biochemistry to ensure the potential participant is suitable for inclusion. If suitable for inclusion after screening medical records, they will be invited for a personal meeting, where all details for the study will be outlined by the investigator or a delegated assistant. The subject will be informed about the opportunity to bring a lay representative in advance of the meeting. The meeting will take place in a closed room without any disturbances, e.g. phone calls. Subjects will be invited for an additional visit at our center to sign the informed consent (IC) form and further screening. After signing the IC, the subject will have blood samples taken for screening. Furthermore, we will assess status of neuropathy with questionnaires and physical examination including biothesiometry, NC-stat-DPNCheck, orthostatic blood pressure and Vagus test, and the subjects will receive equipment and instruction for the 24-hour urine sample to collect before the study day.

The subjects must be fully informed of their rights and responsibilities while participating in the trial as well as possible disadvantages of potential risks. The investigator must ensure the subject has ample time to come to a decision whether to participate in the trial. A voluntary, signed, and personal dated IC must be obtained from the subject before any trial-related activity. The responsibility for seeking IC must remain with the investigator, but the task may be delegated by the investigator to a medically qualified person, in accordance with local requirements. The IC must be signed and personally dated by the person who seeks the IC before any trial-related activity. Subjects will be informed that information given in relation to the project before signing the IC will be passed on to the investigator.

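### Section 9.2 rules out any risk of hypoglycaemia, but the study requires a fasting blood sample and does not exclude users of insulin or sulphonylureas

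*Protocol*

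**What the plan says.** Protocol section 9.2 describes the project as mainly observational, without interventions, and then says: "No changes/adjustments in medication will be made and there will be no risk for hypo/hyperglycemia". Its entry for blood and urine samples describes the hazards of the blood draw as "Almost negligible risk of infection, small bleeding, or pain around syringe insertion".

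The study-day sample list in section 4.5 (Laboratory assessments) includes "Fasting-C-peptide and fasting P-glucose (for HOMA2-%B and -IR").

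Section 4.2 sets 21 exclusion criteria. None of them concerns glucose-lowering drugs.

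The protocol also has general safeguards:
- Section 9.1, before inclusion: "Medical records will be assessed for information on comorbidities and diabetes complications, relevant diagnostic imaging, medications, and previous biochemistry".
- Section 4.2, exclusion criterion 9, which turns on the investigator's view: "Terms according to investigators judgement that makes subjects unsuitable to participate".
- Section 9.2: "To minimize the risk of side effects the examinations will be conducted by trained personnel".

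**The concern.** Section 9.2 is the protocol's list of what could happen to a participant, and section 9.1 requires participants to be told about the tests and their risks. An unqualified denial of risk in that list should be true of every procedure in the study. This one pairs unchanged medication with an absence of glycaemic risk, as if the first secured the second. For a participant who takes insulin or a sulphonylurea and attends fasting because the study asks for it, it does not: the usual medicine without the usual food is the situation in which hypoglycaemia can arise.

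What is at stake is the accuracy of a safety statement that may be carried into the consent material. The concern is with the hypoglycaemia half of the sentence only.

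**Working it through.** There is no power, error-rate or sample-size figure to reproduce here. The check sets the relevant parts of the protocol side by side.

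1. **Does the study require a fast?** Yes. Section 4.5 labels C-peptide and plasma glucose as fasting samples, for the HOMA2 indices. Only these two carry the label, but they are on the same study-day list as the other bloods, so participants have to attend fasting. The length of the fast is not stated.

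2. **Can users of insulin or sulphonylureas take part?** Yes, by inference from the complete list of exclusions.
   - Exclusion criteria in section 4.2: 21.
   - Criteria that concern glucose-lowering drugs: 0.
   - Inclusion criterion 3 treats a response to oral antidiabetic drugs as support for the diagnosis, so treated participants are expected.
   - The aims in section 3 include insulinopenic and severe insulin-deficient phenotypes, which makes insulin users plausible participants.

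3. **Does unchanged medication remove the risk?** No. It removes the risk from altering treatment. The fast is a separate exposure that the study adds on top of unchanged treatment.

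4. **Is the statement qualified elsewhere?** No. The blood-sample entry names three hazards (infection, small bleeding, pain), and none relates to fasting. The volumes in that entry do agree with section 4.5: 4 ml at screening + 84 ml on the study day = 88 ml, and 88 + 24 = 112 ml with the optional biobank sample.

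5. **Is the risk too small for this list?** Not by the section's own standard. For the scans it reports a theoretical rise in lifetime cancer risk from about 25% to less than 25.00002%, that is, less than 25.00002 − 25 = 0.00002 percentage points. Section 2.2 also names hypoglycaemia among the contributors to falls in diabetes, so the protocol recognises it as relevant to this population.

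Steps 1, 2 and 4 are read from the text. Step 3 rests on clinical reasoning, and the documents give no rate to attach to it.

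**The case against.** The strongest reply is that the sentence should be read in context. It follows a statement that the project involves no interventions, so its natural meaning is that the study adds no glycaemic risk through treatment changes. On that reading the wording is loose, not false. This softens the point but does not answer it, because the fast is also something the study adds and the sentence is not limited to treatment changes.

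A second reply is that the size of the risk cannot be shown from the protocol. That stands. The number of users, the length of the fast and the rate of hypoglycaemia are all absent, and eligibility is inferred from the lack of an exclusion. The point therefore concerns the word *no*, not any particular level of risk.

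A third reply is that safeguards exist. They do, and they act before or during the visit. None is specific to fasting, and reducing a risk does not make it nil.

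A reader might go further and infer that participants are left without guidance on food and medicines for the fasting morning. For antihypertensives, section 4.5 does say "then the medication should be taken as usual prior to assessing vital signs", and it has no counterpart for glucose-lowering drugs. But such guidance may well be in the participant information or be given at the personal meeting described in section 9.1. The participant information is not shown, so the protocol does not support that stronger reading. Nor does it show that the fasting draw comes late in the visit or that functional tests are done unfed.

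**Conclusion.** The absolute statement in section 9.2 is not supported by the study's own procedures and eligibility rules, and the blood-sample entry is incomplete in the same respect. The point is minor: the risk is low and unquantified, and endpoints, sample size and analysis are untouched.

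The conclusion rests on two assumptions. The first is that some participants will use insulin or sulphonylureas, which the criteria allow but the protocol does not state. The second is that fasting on an unchanged dose of these drugs carries some risk above zero, which is clinical judgement.

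A reader might infer a material safety hazard, especially since section 4.2 recruits people with autonomic neuropathy and excludes on kidney function only below an eGFR of 15. The protocol gives nothing from which to size such a hazard, so the finding stops at the wording.

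**What to change.** In section 9.2, replace the sentence with: *No changes in medication will be made. Because blood is drawn fasting, there is a low risk of hypoglycaemia, mainly in participants using insulin or sulphonylureas.* Add the same risk to the blood-sample entry, and check that the participant information agrees. If that document already warns of hypoglycaemia, section 9.2 should be brought into line with it. If it does not, it needs the same correction.

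An optional precaution, for the sponsor's clinicians to decide, is to take the fasting sample first and offer food afterwards. If this is adopted, conditions should be the same for all participants before the functional tests, because physical function and postural control are study outcomes. Clinic staff may already work this way.

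The cost is one sentence, one list item and one consistency check. The optional step would add a fixed first procedure and a short break.

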2.2. State of the art

The increased fracture burden in diabetes might partially be explained by an increased risk of falls and by alteration in the fall mechanism. A meta-analysis by Yang et. al. ¹⁵ showed that older persons with diabetes has increased risk of falls compared with healthy controls. Several risk factors that contribute to falls in diabetes exists. These include impaired postural control and gait, diabetic neuropathy, impaired vision, vestibular disorder, cardiovascular disease, comorbidity including hypertension, drugs and hypoglycemia¹⁶. Furthermore, patients with T2D has a higher risk of sarcopenia¹⁷ and decreased muscle function¹⁸, which has been proposed as a contributor to increased fall tendency¹⁹ and increased risk of fractures²⁰. Several studies of diabetes and fracture risk have included data on falls. In these studies, higher fracture risk associated with T2D persisted even after adjustment for increased frequency of falls²¹⁻²³. This suggest that additional underlying mechanisms such as decreased bone quality is involved in the increased fracture risk in T2D. Bone quality is affected by bone mass, bone turnover and bone material properties.

It is suggested that advanced glycation end products (AGEs) produced in response to hyperglycemia are incorporated in the bone structure, hence reducing the material and biomechanical properties of bone by stiffening the bone collagen and reducing bone strength²⁴. Furthermore, the hyperglycemia triggers hypermineralization in the bone causing high BMD²⁵. The interplay between bone and glucose metabolism is complex and not fully understood. An interaction is present between osteocalcin, which is a bone formation marker, but also interacts with insulin sensitivity, thus forming a bone-beta-cell axis^{26,27}. T2D is associated with decreased bone turnover caused by osteocyte dysfunction^{28,29}. It has been suggested that the low bone turnover in T2D cause microcracks, thereby increasing fracture risk³⁰. Bone Material Strength index (BMSi) is measured by microindentation and is reported to be decreased in T2D^{31,32}, which is considered to reflect decreased ability of bone to resist microcrack generation and propagation³³.

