Shanbhoug et al.⁴⁵ found that the observed cortical deficits were a characteristic of the T2D patients with microvascular complications rather than all T2D patients. However, the study was not able to perform an adequate assessment of the separate roles and severity of neuropathy, retinopathy, and nephropathy in bone structure due to limited sample size. A meta-analysis by Liu et al.⁴⁷ reported that T2D patients with diabetic neuropathy have an increased risk of developing osteoporosis and fragility fractures with an OR of 2.15 (95% CI 1.56-2.97). Contrastingly, a Danish study by Khan et al.⁴⁸ using patients enrolled in the Danish Center for Strategic Research in Type 2 Diabetes (DD2) cohort were not able to find a significant association between diabetic neuropathy and fractures. However, they did find an increased risk of falling. A well-powered retrospective study by Lee et. al⁴⁹ found that older male Veterans with diabetes (>98% had T2D) have an increased risk of any fractures and hip fractures, and diabetic neuropathy was reported to be the most important mediator of fracture risk observed in their cohort. A histomorphometry study in humans with high bone turnover showed that the nerve profiles density was 5-fold higher in the intracortical pores compared to bone marrow and periosteum, and the authors suggest an anatomical link between innervation and bone remodeling⁵⁰. Overall, there seems to be a higher fracture risk in subjects with T2D and diabetic neuropathy, which is a very common complication of T2D. However, the exact mechanisms behind this remain to be elucidated.

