Multiple studies have investigated the effects of antidiabetic medication on fracture risk. Several studies found an association on glitazones and increased fracture risk⁵¹⁻⁵³. Evidence of the effect on insulin on fracture risk in T2D is more conflicting, as insulin use have shown both increased^{13,54,55}, neutral⁵⁶ and decreased⁵⁷ outcome on fracture risk. Also sulphonylureas are reported to have both neutral^{53,58,59}, negative^{60,61}, or perhaps even protective⁵⁷ effect on fractures risk. Other medications have been associated with a decreased or neutral effect on the risk of fractures in T2D, such as Metformin^{51,53,57,58}, DDP-4 inhibitors^{56,62,63}, GLP-1 receptor agonists^{62,64} and SGLT-2 inhibitors^{65,66}. In addition, concomitant medications related to comorbidities might also play a role in fracture risk in T2D. Thiazides have been associated with a decreased fracture risk, while loop diuretics are associated with higher fracture risk⁶⁷. An updated meta-analysis revealed no significant effect of statin treatment on the risk of fractures⁶⁸. Also drugs commonly

used for diabetic neuropathy such as tricyclic antidepressants^{69,70} and γ -aminobutyric acid (GABA) analogs⁶⁹ are associated with increased risk of falls and fracture.

[figure not shown]

Figure 1: Factors leading to increased fracture risk in T2D

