A commercially available handheld device (Vagus™, Medicus Engineering Aps, Aarhus N, Denmark) will be used to test the autonomic nervous system and hereby the autonomic neuropathy. The participant will hold the device during four steps, where the device will 1) measure the heart rate at rest, 2) measure the heart rate response from laying position to standing position, 3) measure the relationship between heart rate during expiration and inspiration, and 4) measure the heart rate conditions during exhalation with a

resistance of 40mmHg and at rest. The latter will not be performed if the subject has known proliferative diabetic retinopathy or other known diseases with risk of retinal bleeding. The test is defined as abnormal if Cardiac Autonomic Neuropathy (CAN)-Score is ≥ 2 .

Estimated time: 15-20 min.

COMPASS-31

A questionnaire about symptoms of autonomic neuropathy (attached). Gives us the opportunity to measure non-invasive and stratify people with and without neuropathy. Will be filled on iPad by the participants, and entries are transferred to REDCap.

Estimated time: 10 min.

Michigan Neuropathy Screening Instrument (MNSI)

MNSI (attached) will be used as a part of the screening process for diabetic neuropathy. MNSI includes two separate assessments: a 15-item self-administered questionnaire (filled in REDCap by the participants) and a lower extremity examination that includes inspection and assessment of vibratory sensation and ankle reflexes. Estimated time: 15 min.

Assessment of muscle strength

Isometric handgrip strength will be assessed by a hand dynamometer (NC70144, Procare.dk, Denmark). Each subject is instructed to exert maximal contraction force with their dominant hand (defined as their “writing hand”), when standing in an upright position and the hand tested pointing downwards, parallel to the body, and unsupported. Each subject repeats the test three times. The maximal contraction level of the three trials is selected for further analysis.

Isometric measurement of knee extension strength will be measured with hand-held dynamometer. Similar procedures as for the arms.

Estimated time: 5 min.

Test for postural control

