9. ETHICAL CONSIDERATIONS

The trial will be conducted in compliance with *Harmonised Tripartite Guideline for Good Clinical Practice (ICH GCP)*⁸⁴ and applicable regulatory requirements, and in accordance with the Helsinki Declaration⁸⁵ for biomedical research involving test subjects. The methods used have been tested and performed in several studies both in Denmark and abroad and no long-term side effects have been reported. The risks associated

with the project are few as low dose radiation is used and the tests imply limited risks. The potential benefits in terms of well-being are large and are estimated to outweigh the potential risks.

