If information becomes available that may be relevant to the subjects willingness to continue participating in the trial, the investigator must inform the subject in a timely manner, and revised IC must be provided and a new IC must be obtained.

Participants have time for reflection and an additional informational meeting (with participating relatives etc.) will be scheduled.

The given information will include:

- That this a scientific project investigating the T2D bone phenotype and potential risk factors of diabetic bone disease including diabetic neuropathy.
- Information regarding the different tests involved including risks.
- That withdrawal from the project is possible at any time.
- That data collected will be published in an anonymized form, without any traces of personal data
- That data collected will be safely stored in accordance with the rules in force.

- The IC gives the investigator, the sponsor, and the sponsor's representatives as well as any supervisory authority direct access to obtain information in the patient's medical record, etc., including electronic medical records, in order to see information about the subject's health conditions, which is necessary as part of the implementation of the research project as well as for control purposes, including self-control, quality control and monitoring, which they are obliged to carry out.

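### Section 9.2 declares the Vagus, force platform and gait tests free of risk, which Section 4.5 contradicts for Vagus and which is too absolute for the balance and walking tests

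*Protocol*

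**What the plan says.** Protocol Section 9.2 lists risks examination by examination. Its final bullet groups vital signs and body measurements, ECG, skin AGE Reader, Vagus, QST, NC-stat DPNCheck and the motor tests, and closes with "force platform, gait function and muscle strength assessments: No risks or side-effects".

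Section 4.5 describes the tests themselves. Vagus has four steps. The second is to "measure the heart rate response from laying position to standing position". The fourth is exhalation against a resistance of 40 mmHg, and of that step the protocol says: "The latter will not be performed if the subject has known proliferative diabetic retinopathy or other known diseases with risk of retinal bleeding". The postural control test has four 35-second conditions, the hardest with closed eyes on foam. The Timed Up and Go test is done at maximum walking speed.

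Section 9.1 says what participants will be told, including "Information regarding the different tests involved including risks".

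**The concern.** A procedure that is withheld from some people on safety grounds cannot also be listed as having no risk. The balance and walking tests raise a similar question. They load the functions that the protocol names as causes of falls, in a sample partly selected for severe neuropathy or for an earlier fracture.

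What is at stake is disclosure. Section 9.2 is where the protocol sets out the risks that Section 9.1 promises to explain. If the participant information follows it, a person with severe neuropathy could be told that standing on foam with closed eyes carries no risk at all.

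**Working it through.** The point rests on comparing statements. The only arithmetic is the share of the sample concerned.

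1. **Vagus, resisted exhalation (direct contradiction).** Section 9.2 puts Vagus in the no-risk bullet. Section 4.5 restricts one of its steps because of retinal bleeding. The restriction applies to known disease only. Section 9.1 places the Vagus test at the screening visit, and its list of screening assessments includes neither OCT nor fundus photography. The text therefore does not show the study's own eye examination coming first, and retinopathy that nobody has yet detected would not trigger the restriction.

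2. **Vagus, lying to standing (inference).** Inclusion criterion 6 in Section 4.2 admits people to the N+ group for autonomic neuropathy, which may be defined by severe orthostatic blood pressure abnormalities. The second Vagus step asks participants to stand up from lying.

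3. **Force platform and gait (inference).** Section 2.2 lists contributors to falls in diabetes: "These include impaired postural control and gait, diabetic neuropathy, impaired vision". It also cites a Danish study of diabetic neuropathy that found no significant association with fractures, and adds: "However, they did find an increased risk of falling". Drugs commonly used for neuropathy "are associated with increased risk of falls and fracture". The postural control text in Section 4.5 foresees that some participants will not complete a 35-second stance: up to three attempts are allowed before a condition is skipped.

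4. **Who is exposed.** From Section 4.2, the N+ group is 40 / 300 = 13.3% of the planned sample and the F+ group is 100 / 300 = 33.3%. The protocol does not state how many F+ participants have neuropathy, and none is assumed here.

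5. **The protocol's own standard of disclosure.** Elsewhere Section 9.2 reports very small risks. Infection, bleeding or pain from blood sampling is described as close to negligible. The lifetime cancer risk from the scans is put at about 25% rising to less than 25.00002%, a difference below 25.00002 − 25 = 0.00002 percentage points. Beside those entries, a flat statement of no risk for balance and walking tests is inconsistent.

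6. **What cannot be computed.** No fall rate during testing is given, so no expected number of falls follows.

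**The case against.** The case on the other side has weight. The retinal hazard is already managed in conduct: people with known disease are spared the step, and Section 9.1 has medical records checked for diabetes complications and relevant imaging before anyone is invited. The no-risk bullet could then be read as describing what remains after that restriction. This lessens the practical hazard, but it does not rescue the wording, because undetected disease remains possible.

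On falls, no section says that these tests carry such a risk. The evidence in Section 2.2 concerns falls in general, not supervised testing, and the meta-analysis cited there concerns older persons while enrolment starts at 40 years. The tasks are short. Running is barred, there is a footwear rule, breaks are planned and a wider stance is allowed. Staff are trained, and exclusion criterion 9 covers reduced physical ability. All of this stands. It supports calling the risk small, not calling it absent.

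Several stronger readings are tempting and should not be drawn:

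- A reader might infer that Section 9 contradicts the bullet outright when it says that "low dose radiation is used and the tests imply limited risks", or that Section 9.2 does so by describing overall risk as very low. Both statements cover the whole set of examinations, including biopsy and microindentation, and a set with limited overall risk can contain tests with none.
- A reader might include orthostatic blood pressure. Section 4.5 gives it its own heading, and the bullet does not name it.
- A reader might infer that a fall would go unrecorded, or that participants are in fact misinformed. The case report form and the participant information are not shown, and Section 9.1 requires subjects to be fully informed of potential risks.

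**Conclusion.** The point holds as a correction of wording with a small safety addition. For Vagus, the no-risk statement is contradicted by the protocol's own restriction in Section 4.5. For the force platform and gait tests and for standing up during Vagus, it is too absolute. That second part is an inference, which assumes that the general link between neuropathy, impaired balance and falls carries over in some degree to the test situation.

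The group most clearly concerned is the 40 N+ participants, followed by the 100 with an earlier fracture. The size of the risk is unknown from the document. Sample size, error rates and analysis are untouched. Priority is low.

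**What to change.** In Section 9.2, take Vagus, the force platform and the gait tests out of the no-risk bullet. Give them an entry of their own that states a small risk of unsteadiness or falling, and that the resisted exhalation is not done in subjects with a known risk of retinal bleeding, in line with Section 4.5. Check that the participant information says the same.

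In Section 4.5, add that the tester already present stays within reach during the closed-eyes and foam stances and during the walking tests. This needs no extra staff, provided that the recording can be run from that position; the protocol does not describe the staffing. The scoring of sway and gait does not change.

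The cost is a few sentences and a check of the participant information. The one downside is a slightly less favourable risk statement.
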